#### 3.5.2 Pharmacokinetic Concentrations

Plasma concentrations for CIVI 007 will be summarized over scheduled time using descriptive statistics. Actual sampling times that are outside the scheduled sampling time window will be excluded from summary statistics but will still be used in the calculation of PK parameters. Individual plasma concentration data versus actual time points will be listed.

For each of the dosing days, the sampling time windows are as follows:

- Pre-dose: -1 hour,
- 3 hours post-dose: ±1 hour, and
- 8 hours post-dose: ±1 hour.

For each study visit, the sampling time window is ±3 days.

Individual concentrations of CIVI 007 will be plotted on a linear and semi-log scale against actual sampling time points for each treatment. Mean (±SD) CIVI 007 concentration will be plotted on a linear and semi-logarithmic scale against nominal time points by treatment.

#### 3.5.3 Pharmacokinetic Parameters

Where possible, standard non-compartmental analyses will be used to calculate the PK parameters of interest for CIVI 007 in section 2.3.3.2. The actual collection times will be used for PK parameter calculation. The Linear Up Log Down method (equivalent to the Linear Up/Log Down option in WinNonlin® Professional) will be used in the computation of AUCs.

The elimination constant rate,  $\lambda_z$ , will not be presented for patients who do not exhibit a terminal elimination phase in their concentration-time profiles. In order to estimate  $\lambda_z$ , linear regression of concentration in logarithm scale versus time will be performed using at least 3 data points. Uniform weighting will be selected to perform the regression analysis to estimate  $\lambda_z$ .

Generally,  $\lambda_z$  will not be assigned if one of the following happens:

- 1. Tmax is one of the 3 last data points,
- 2. The adjusted regression coefficient (R-squared) is less than 0.80,
- 3. The estimated  $\lambda_z$  indicates a positive slope, or
- 4. The terminal elimination phase is not linear (as appears in a semi-logarithmic scale) based on visual inspection.

If the  $\lambda_z$  is not assigned, the values of associated PK parameters will not be calculated. In the cases where AUCextrap exceeds 20%, the  $\lambda_z$  will be assigned and the  $\lambda_z$  and the corresponding  $\lambda_z$ -related PK parameters will be flagged but still included to the summary statistics with an explanatory footnote.

Pharmacokinetic parameters of CIVI 007 will be listed and summarized using descriptive statistics.

Where sufficient data are available, CIVI 007 fold-increase in exposure will be examined between the dose cohorts. The PK parameters may be analyzed for dose proportionality using analysis of variance model, as appropriate.

# 3.6 Safety Assessment

Safety data will be summarized descriptively by actual treatment received (and in total for selected analyses) based on the Safety Analysis Population. All the individual data will be listed.

# 3.6.1 Adverse Events (AEs)

AEs will be monitored and documented from the time of screening until completion of the Day 85 Visit, early termination visit or extended Follow-up, whichever is later. All AEs will be coded to system organ class and preferred term using MedDRA terminology version 22.0 (or the most recent version available).

Treatment-emergent adverse events (TEAEs) are defined as AEs that worsen in severity or relationship to study drug or start on or after the time of start of first study drug administration.

Adverse events of special interest (AESIs) include CTCAE Version 5.0 Grade 2 or higher ALT measurements, and injection site reactions (ISRs).

An overview of AEs will be provided including counts and percentages of patients (and event counts) with the following:

• Any AEs (overall and by maximum severity)

- Any drug related AEs (overall and by maximum severity)
- Any AEs of special interest (ALT and injection site reactions)
- Any serious AEs (SAEs)
- Any AEs leading to discontinuation of study treatment
- Any AEs leading to discontinuation of study
- Any AEs leading to death

The primary endpoint is the incidence and severity of any drug-related AEs. The number and percentage of patients who experience 1 or more drug-related (possibly, probably, or definitely related) AEs will be presented by system organ class and preferred term by overall and by maximum severity. In addition, summaries will be provided by system organ class, preferred term, and maximum severity.

Listings of patients with drug-related AEs will be presented.

Counts and percentages of patients (and event counts) will also be presented by system organ class and preferred term for each of the categories in the overview.

Listings will be presented for all AEs, specifically for AESIs, SAEs and AEs leading to death.

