6.3.4 Day 85 or Early Termination

The following procedures will be performed at Day 85 or early termination:

- Perform full physical examination.
- Record vital signs and weight.
- Collect urine urinalysis assessment.
- Perform urine pregnancy test.
- Collect blood samples for clinical safety chemistry panel, coagulation, and hematology assessments.
- Collect blood samples for fasting lipid panel assessment.
- Collect blood samples for fasting apolipoproteins and LDL-C (beta-quant).
- Collect blood samples for hsCRP, PCSK9, and fibrinogen analysis.
- Collect blood samples for anti-drug antibody analysis
- Collect blood samples for sparse PK, cytokine panel and complement activation analysis.
- Perform 12-lead ECG measurements
- Record adverse events.

Record concomitant medications.

Extended Follow-up Visits

Extended follow-up visits will be conducted based on either LDL-C level at Day 85 or for safety considerations at the Investigator's discretion.

- If Day 85 LDL-C levels are <80% of their baseline level; extended follow-up will occur monthly for 3 months and end earlier if LDL-C levels are ≥80% of baseline. The fasting lipid panel will be assessed and occur monthly for up to 3 months or until LDL-C returns to within 80% of its baseline level (whichever is sooner). Those visits will also record AEs and concomitant medication.
- Extended Follow-up visits for safety considerations (frequency and assessments will be at the discretion of the Investigator) to monitor Investigator determined safety considerations may also occur and extend beyond 3 months, if deemed appropriate by the Investigator, and will continue until there are no safety observations requiring further follow-up. Those visits will also record AEs and concomitant medication.

For extended follow-up Visits due to LDL-C <80% of the baseline level. The procedures need to be performed will include the following:

- Record vital signs and weight.
- Collect blood samples for fasting lipid panel assessment.
- Record adverse events.
- Record concomitant medications.

For extended follow-up Visits for safety considerations, the procedures need to be performed will be consideration specific and may include but not be limited to the following:

- Record vital signs and weight.
- Collect urine sample for urinalysis assessment.
- Collect blood samples for clinical safety chemistry panel, coagulation, and hematology assessments.
- Perform 12-lead ECG measurements.
- Record adverse events.

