8.2 Adverse Events

An adverse event is defined as any untoward medical occurrence in a clinical investigation patient administered a pharmaceutical product, which does not necessarily have a causal relationship with this treatment. An adverse event can therefore be any unfavorable and/or unintended sign (including an abnormal laboratory finding), symptom, or disease temporally associated with the use of an IMP, whether or not related to the IMP. All adverse events, including observed or volunteered problems, complaints, or symptoms, are to be recorded on the appropriate eCRF.

Adverse events, which include clinical laboratory test variables, will be monitored and documented from the time of screening until completion of the Day 85 Visit, early termination visit or extended Follow-up, whichever is later. Patients should be instructed to report any adverse event that they experience to the Investigator, whether or not they think the event is due to study treatment. Beginning at screening, Investigators should make an assessment for adverse events at each visit and record the event on the appropriate adverse event eCRF.

Wherever possible, a specific disease or syndrome rather than individual associated signs and symptoms should be identified by the Investigator and recorded on the eCRF. However, if an observed or reported sign or symptom is not considered a component of a specific disease or syndrome by the Investigator, it should be recorded as a separate adverse event on the eCRF. Additionally, the condition that led to a medical or surgical procedure (e.g., surgery, endoscopy, tooth extraction, or transfusion) should be recorded as an adverse event, not the procedure itself.

Any medical condition already present at Screening, should be recorded as medical history and not be reported as an adverse event unless the medical condition or signs or symptoms present at baseline changes in severity, frequency, or seriousness at any time during the study. In this case, it should be reported as an adverse event.

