Appendix A: Schedule of Procedures

	Screeninga	g ^a Treatment Period ^b				Follow-up Period ^c				
Procedure/Visit	Up to Day -21	Day 1 ^d	Day 8	Day 15	Day 22	Day 29	Day 36	Day 43	Day 57	Day 85 or ET
Visit #	1	2	3	4	5	6	7	8	9	10
Informed consent	X									
Inclusion/exclusion criteria	X									
Medical/surgical history and demographics	X									
Full physical examination	X									X
Symptom-directed physical examination		X	X	X	X	X	X	X	X	
Vital signs ^e , height ^f , and weight	X	X	X	X	X	X	X	X	X	X
Urinalysis ^g	X	X	X	X	X	X	X	X	X	X
FSH/Serum/Urine pregnancy test ^h	X	X	X	X	X	X	X	X	X	X
Clinical safety chemistry panel, coagulation, and hematology	X	X	X	X	X	X	X	X	X	X
Drug Screen/ TSH, HbA1c, and serologyi	X									
Fasting lipid panel ^j	X	X	X	X	X	X	X	X	X	X
Fasting apolipoproteins & beta quant LDL-Ck		X	X	X		X	X	X	X	X
hsCRP, PCSK9, and fibrinogen		X	X	X	X	X	X	X	X	X
Randomization		X								
Study drug/Placebo administration		X				X				
Sample for antidrug antibodies		X		X		X		X	X	X
Sparse PK, cytokine and complement activation sampling ¹		X	X	X	X	X	X	X	X	X
12-lead ECG ^m	X	X		X		X			X	X
Concurrent statin PK ⁿ		X				X			X	
Adverse events (including injection site reactions)	X	X	X	X	X	X	X	X	X	X
Concomitant medications	X	X	X	X	X	X	X	X	X	X

Footnotes are on the next page.

- ^a All eligible patients will partake in the Screening Visit up to 21 days prior to Day 1.
- b.c Study assessments will be completed within ±3 days of the given time point for all study visits other than Day 1. Extended follow-up beyond day 85 for below baseline LDL-C will assess the fasting lipid panel and occur monthly for up to 3 months or until LDL-C returns to within 80% of its baseline level. Those visits will also record AEs and concomitant medication
- d The Investigator will query the participant on Day 1 to determine if there have been any changes in the participant's health that would affect eligibility or require an update to his/her medical/surgical history.

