Extended follow-up visits will be conducted on a monthly basis for up to 3 months if Day 85 LDL-C levels are <80% of their baseline level; extended follow-up will end within the 3-month period if LDL-C levels are ≥80% of baseline. Extended follow-up visits (frequency and assessments will be at the discretion of the Investigator) to monitor Investigator determined safety considerations may extend beyond 3 months, if deemed appropriate by the Investigator, and will continue until there are no safety observations requiring further follow-up. The total duration of the study for each patient will be approximately 3 to 6.5 months, depending on the length of the screening, and follow up periods.

The study design is graphically summarized below:

Patients will be routinely monitored for safety, tolerability and pharmacodynamic effects. The schedule of procedures and clinical laboratory analytes are detailed in Appendices of the protocol: measurements will be taken as detailed in Appendix A (schedule) and Appendix B (clinical laboratory analytes).

CiVi Biopharma, Inc. Protocol: CIVI 007-2-01

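### AE tables by arm count every recorded event, but follow-up past Day 85 depends partly on LDL-C response, so active patients are likely to be observed longer (low-end minor)

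*SAP*

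**What the plan says.** **Recording window.** SAP 3.6.1 documents AEs "from the time of screening until completion of the Day 85 Visit, early termination visit or extended Follow-up, whichever is later"; Protocol 8.2 has the same open end. A treatment-emergent AE is one that worsens or that begins at a stated point, "start on or after the time of start of first study drug administration". The definition has a start and no end.

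**Tables.** SAP 3.6 presents safety data descriptively by actual treatment. SAP 3.6.1 gives counts and percentages of patients, with event counts, for any AE, drug-related AEs, AEs of special interest, serious AEs, discontinuations and deaths. Drug-related AEs are a primary endpoint, reported as the number and percentage of patients with at least one.

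**Two routes into extended follow-up (SAP 2.2.1).** The first is LDL-C response: visits are "conducted on a monthly basis for up to 3 months if Day 85 LDL-C levels are <80% of their baseline level". The second is investigator safety considerations, possible in any arm, where visits "may extend beyond 3 months, if deemed appropriate by the Investigator, and will continue until there are no safety observations requiring further follow-up".

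**What happens at those visits.** The Extended Follow-up Visits text after Protocol 6.3.4 says, for both routes, "Those visits will also record AEs and concomitant medication". The procedure list introduced by "For extended follow-up Visits due to LDL-C <80% of the baseline level. The procedures need to be performed will include the following" holds only vital signs and weight, a fasting lipid panel, AEs and concomitant medication.

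**The concern.** The LDL-C trigger is a measure of response. Protocol 3.2 describes dose-dependent lipid lowering, so more active than placebo patients can be expected to meet it. Someone followed longer has more time to record an event. A crude percentage or event count then rises on active treatment even when the true risk is the same.

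This touches a primary endpoint that will be read by eye across arms of about 12, with no AE test. The direction is against the drug. Neither the SAP nor Protocol 9.2.1 cuts the AE tables at Day 85, separates later events or adjusts for observation time. SAP 3.3.7 summarizes days in study by treatment but does not link them to the AE tables, and its top category is 85 days or more.

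**Working it through.** **1. How much longer can a patient be observed?** The plan's own figure is a total duration of about 3 to 6.5 months. At 30.44 days per month:
- Longest: 21 (screening) + 84 (Day 1 to Day 85) + 91.3 (3 months) = 196.3 days = 6.45 months.
- Shortest: 84 days = 2.76 months, or 105 days = 3.45 months with full screening.

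The stated range reproduces, and its upper end includes the full 3-month extension. From first dose, a fully extended patient is observed for 85 + 91.3 = 176.3 days against 85, a ratio of 2.07.

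**2. Is detection the same after Day 85?** No. Appendix A schedules "Clinical safety chemistry panel, coagulation, and hematology", urinalysis and a physical examination at all eight visits from Day 8 to Day 85, and ECGs at four of them. LDL-C-triggered visits are monthly and list none of these. Protocol 8.2 counts as an AE "any unfavorable and/or unintended sign (including an abnormal laboratory finding), symptom, or disease temporally associated", so fewer laboratory AEs can be found. The last dose is on Day 29, so this extension starts 85 − 29 = 56 days after it.

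**3. Which rows are exposed?** Any AE, serious AEs and event counts most; drug-related AEs slightly. Dosing is over, so treatment discontinuation should not arise and new injection site reactions are unlikely. ALT events and the laboratory primary endpoint need tests that the LDL-C-triggered visits do not list.

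**4. Illustrative size.** The documents give neither the share extended nor an AE rate, and describe human lipid effects only to 4 weeks after dosing (Protocol 3.2). All inputs below are therefore assumed, with equal true hazards in all arms.
- p = incidence by Day 85 (5% or 40%); e = extra days (30 or 90); f = hazard multiplier after Day 85 (0.25 or 1); s = share extended (active 70% or 40%, placebo 8%).
- h = −ln(1 − p)/85.
- Incidence if extended: P = 1 − (1 − p)·exp(−h·f·e).
- Spurious difference = (s_active − s_placebo)·(P − p).
- Event-count ratio = (85 + s_active·e·f)/(85 + s_placebo·e·f).

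Example with p = 0.40, e = 90, f = 0.25, 70% vs 8%: h = 0.00601; P = 1 − 0.60·exp(−0.1352) = 0.4759; difference = 0.62 × 0.0759 = 4.70 points, or 0.56 patient per 12. Event-count ratio = 100.75/86.8 = 1.161.

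| Quantity | 70% vs 8%, f = 0.25 | 40% vs 8%, f = 0.25 | 70% vs 8%, f = 1 | 40% vs 8%, f = 1 |
|---|---|---|---|---|
| Difference in points, p 5%, 30 days | 0.27 | 0.14 | 1.06 | 0.55 |
| p 5%, 90 days | 0.79 | 0.41 | 3.11 | 1.61 |
| p 40%, 30 days | 1.64 | 0.85 | 6.14 | 3.17 |
| p 40%, 90 days | 4.70 | 2.43 | 15.54 | 8.02 |
| Event-count ratio, 30 days | 1.054 | 1.028 | 1.213 | 1.110 |
| Event-count ratio, 90 days | 1.161 | 1.083 | 1.605 | 1.312 |

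The f = 0.25 columns suit drug-related AEs better. The f = 1 columns assume a constant hazard and equal detection.

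**5. None of these is a bound.** At 100% vs 0% extended, p = 40%, 90 days and f = 1: P = 1 − 0.60^(175/85) = 0.651, a difference of about 25 points, and the ratio is 175/85 = 2.06. The same shares with f = 0.25 give 47.6 − 40 = 7.6 points.

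**6. Against chance.** The standard error of a difference with 12 per arm is √(2p(1 − p)/12): 8.9 points at 5% and 20.0 points at 40%.

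**7. Would one rate over all follow-up cure it?** No. With f = 0.25, the event-count ratio times (85 + s_placebo·e)/(85 + s_active·e) gives 0.869 (30 days) and 0.723 (90 days) at 70% vs 8%, and 0.926 and 0.825 at 40% vs 8%. Equal true risk would then appear to favour the drug.

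**The case against.** The case on the other side is about weight.
- Safety analysis is descriptive, with no AE test to distort. This stands, but with about 12 per arm the raw percentages are what readers compare.
- Counting every recorded AE is a legitimate, conservative choice, since the bias runs against the drug. This also stands, and is why late events must stay visible.
- Days in study are summarized by treatment and all AEs are listed, so a careful reader could detect the imbalance. True, but that displays unequal follow-up without correcting the tables.
- Protocol 8.2.3 makes time since dosing part of the causality judgement, which limits late drug-related events further. This stands.
- A cut at the Day 85 visit is not a strictly common end day: visits have a ±3-day window and early terminators stop sooner. Correct, but that residue is small beside an extension of up to 3 months.

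Three stronger readings might be inferred, and the documents do not support them. One is that the analysis window is left open to be chosen later: read plainly, SAP 3.6.1 counts everything recorded, so the window is stated, though it differs by patient. Another is that the whole AE output, or the primary endpoint, is seriously biased: several rows can hardly be affected, and the primary row probably only slightly. The third is that the constant-hazard figures are a ceiling: step 5 shows larger values, and the safety route has no time cap.

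**Conclusion.** The point holds at the low end of minor. Followed as written, the plan lets observation time depend on response to treatment and then compares arms on measures that grow with observation time. The likely direction is against the drug, but imbalance is expected rather than certain: a placebo patient can fall below 80% of baseline, and safety extensions can occur in any arm.

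The true size cannot be derived from the documents. In the falling-hazard scenarios the spurious difference is 0.1 to 4.7 points (0.02 to 0.56 patient per 12) and the event-count ratio 1.03 to 1.16, below the sampling error of a two-arm difference. The constant-hazard scenarios, 0.55 to 15.5 points and a ratio of 1.11 to 1.61, fit any-AE rows better than the primary endpoint. No conclusion of the trial is likely to turn on this; the case for change is that the remedy is cheap.

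**What to change.** In SAP 3.6.1, base the between-arm AE comparison, including drug-related AEs, on treatment-emergent AEs with onset or worsening from first dose through the Day 85 visit, or early termination if earlier. Accept the ±3-day visit window. With equal hazards and similar early termination, arms then show equal expected percentages and an event-count ratio of 1.

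Directly beside it, show AEs with onset or worsening after Day 85 by arm, with the number of patients extended, the trigger and the patient-time, so that every recorded AE is still reported. State that this later period covers only extended patients and is not a randomized comparison. If rates are given, give them separately for the two periods, and do not use one whole-follow-up rate.

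The cost is SAP wording, one onset-date flag and one added table; visits and data collection do not change. The downside is that late events leave the main table for a drug that Protocol 1.1 describes as long-lived in the liver, so the second table must sit next to the first.

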#### 3.6.2 Clinical Laboratory Tests

Clinical safety chemistry, hematology, coagulation, and urinalysis will be collected at each study visit. Fibrinogen, cytokine and complement activation sampling will be collected at Day 1, Day 8, Day 15, Day 22, Day 29, Day 36, Day 43, Day 57 and Day 85 or early termination. hsCRP will be collected at Day 1, Day 8, Day 15, Day 22, Day 29, Day 36, Day 43, Day 57 and Day 85 or early termination. Thyroid-stimulating hormone (TSH), hemoglobin A1c (HbA1c), and serology will be collected in the Screening Visit.

Observed values and changes from baseline will be presented at each scheduled visit and baseline by laboratory test.

The primary endpoint is the incidence of clinically significant laboratory abnormalities, based on changes from baseline in hematology, clinical safety chemistry, and urinalysis test results. The incidence of abnormalities will be summarized with counts and percentages of patients for selected parameters grading by Common Terminology Criteria for Adverse Events (CTCAE) Version 5.0 if appropriate.

Laboratory	CTCAE Term	Grade 1	Grade 2	Grade 3	Grade 4
Chemistry	Alanine aminotransferase increased	>ULN - 3.0 x ULN if baseline was normal;	>3.0 - 5.0 x ULN if baseline was normal;	>5.0 - 20.0 x ULN if baseline was normal;	>20.0 x ULN if baseline was normal;
		1.5 - 3.0 x baseline if baseline was abnormal	>3.0 - 5.0 x baseline if baseline was abnormal	>5.0 - 20.0 x baseline if baseline was abnormal	>20.0 x baseline if baseline was abnormal
	Aspartate aminotransferase increased	>ULN - 3.0 x ULN if baseline was normal;	>3.0 - 5.0 x ULN if baseline was normal;	>5.0 - 20.0 x ULN if baseline was normal;	>20.0 x ULN if baseline was normal;
		1.5 - 3.0 x baseline if baseline was abnormal	>3.0 - 5.0 x baseline if baseline was abnormal	>5.0 - 20.0 x baseline if baseline was abnormal	>20.0 x baseline if baseline was abnormal

Laboratory	CTCAE Term	Grade 1	Grade 2	Grade 3	Grade 4
	Blood bilirubin	Total Bilirubin	Total Bilirubin	Total Bilirubin	Total Bilirubin
	increased	>ULN - 1.5 x ULN if baseline was normal;	>1.5 - 3.0 x ULN if baseline was normal;	>3.0 - 10.0 x ULN if baseline was normal;	>10.0 x ULN if baseline was normal;
		> 1.0 - 1.5 x baseline if baseline was abnormal	>1.5 - 3.0 x baseline if baseline was abnormal	>3.0 - 10.0 x baseline if baseline was abnormal	>10.0 x baseline if baseline was abnormal
	Alkaline phosphatase increased	>ULN - 2.5 x ULN if baseline was normal;	>2.5 - 5.0 x ULN if baseline was normal;	>5.0 - 20.0 x ULN if baseline was normal;	>20.0 x ULN if baseline was normal;
		2.0 - 2.5 x baseline if baseline was abnormal	>2.5 - 5.0 x baseline if baseline was abnormal	>5.0 - 20.0 x baseline if baseline was abnormal	>20.0 x baseline if baseline was abnormal
	Creatinine increased	>ULN - 1.5 x ULN	>1.5 - 3.0 x baseline; >1.5 - 3.0 x ULN	>3.0 x baseline; >3.0 - 6.0 x ULN	>6.0 x ULN
	CPK increased	>ULN - 2.5 x ULN	>2.5 x ULN - 5 x ULN	>5 x ULN - 10 x ULN	>10 x ULN
	Hyperkalemia	Potassium	Potassium	Potassium	Potassium
		>ULN - 5.5 mmol/L	>5.5 - 6.0 mmol/L	>6.0 - 7.0 mmol/L	>7.0 mmol/L
	Chronic kidney	eGFR	eGFR	eGFR	eGFR
	disease	<lln -="" 60
ml/min/1.73 m2 or proteinuria 2+ present; urine protein/creatinine >0.5'.</lln>	59 - 30 ml/min/1.73 m2	29 - 15 ml/min/1.73 m2	<15 ml/min/1.73 m2
Hematology	Anemia	Hemoglobin (Hgb)	Hemoglobin (Hgb)	Hemoglobin (Hgb)	
		<lln -="" 10.0="" dl;
<lln -="" 6.2="" l;
<lln -="" 100="" g="" l<="" td=""><10.0 - 8.0 g/dL; <6.2 - 4.9 mmol/L; <100 – 80 g/L	<8.0 g/dL; <4.9 mmol/L; <80 g/L		</lln></lln></lln>	<10.0 - 8.0 g/dL; <6.2 - 4.9 mmol/L; <100 – 80 g/L	<8.0 g/dL; <4.9 mmol/L; <80 g/L	
	Hemoglobin increased	Hemoglobin > ULN &	Hemoglobin > ULN &	Hemoglobin > ULN &	
		Increase in >0 - 2 g/dL	Increase in >2 - 4 g/dL	Increase in >4 g/dL	
	White blood cell decreased	<lln -="" 3000="" mm3;
<lln -="" 10e9="" 3.0="" l<="" td="" x=""><3000 - 2000/mm3; <3.0 - 2.0 x 10e9 /L	<2000 - 1000/mm3; <2.0 - 1.0 x 10e9 /L	<1000/mm3; <1.0 x 10e9 /L	</lln></lln>	<3000 - 2000/mm3; <3.0 - 2.0 x 10e9 /L	<2000 - 1000/mm3; <2.0 - 1.0 x 10e9 /L	<1000/mm3; <1.0 x 10e9 /L
	Platelet count decreased	<lln -="" 75,000="" mm3;
<lln -="" 10e9
/L</lln></lln>	<75,000 - 50,000/mm3; <75.0 - 50.0 x 10e9 /L	<50,000 - 25,000/mm3; <50.0 - 25.0 x 10e9 /L	<25,000/mm3; <25.0 x 10e9 /L

For the other parameters, the incidence of abnormalities (as defined by normal ranges) prior to the first dose of study drug and after the first dose of study drug will be summarized with counts and percentages of subjects.

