7 EFFICACY ASSESSMENTS

7.1 Primary Endpoints

The primary safety/tolerability endpoints for this study are as follows:

- incidence and severity of any drug-related AE
- incidence of clinically significant laboratory abnormalities, based on drug-induced changes from baseline in hematology, clinical safety chemistry, and urinalysis test results.

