Clinically significant abnormal laboratory or other examination (e.g., ECG) findings that are detected during the study or are present at Screening, and significantly worsen during the study should be reported as adverse events, as described below. The Investigator will exercise his or her medical and scientific judgment in deciding whether an abnormal laboratory finding or other abnormal assessment is clinically significant. Clinically significant abnormal laboratory values occurring during the clinical study will be followed until repeat tests return to normal, stabilize, or are no longer clinically significant. Abnormal test results that are determined to be an error should

not be reported as an adverse event. Laboratory abnormalities or other abnormal clinical findings (e.g., ECG abnormalities) should be reported as an adverse event if any of the following are applicable:

- If an intervention is required as a result of the abnormality
- If action taken with the study drug is required as a result of the abnormality
- Based on the clinical judgment of the Investigator

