# 2.3 Study Endpoints

# 2.3.1 Primary Safety/Tolerability Endpoints

The primary safety/tolerability endpoints for this study are as follows:

· incidence and severity of any drug-related AE

 incidence of clinically significant laboratory abnormalities, based on drug-induced changes from baseline in haematology, clinical safety chemistry, and urinalysis test results.

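### SAP 3.6.2 does not tabulate the second primary endpoint as named: its counts carry no clinical-significance rule and, for many tests, include abnormalities unchanged since Day 1

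*SAP*

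**What the plan says.** Protocol 7.1 defines the second primary endpoint as "incidence of clinically significant laboratory abnormalities, based on drug-induced changes from baseline in hematology, clinical safety chemistry, and urinalysis test results". SAP 2.3.1 repeats it. SAP 3.6.2 restates it without the drug-induced qualifier: "The primary endpoint is the incidence of clinically significant laboratory abnormalities, based on changes from baseline in hematology, clinical safety chemistry, and urinalysis test results".

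In SAP 3.6.2, the next sentence gives the counting rule for tests in its CTCAE Version 5.0 table: "The incidence of abnormalities will be summarized with counts and percentages of patients for selected parameters grading by Common Terminology Criteria for Adverse Events", to be applied where appropriate. For the remaining tests the SAP summarizes "the incidence of abnormalities (as defined by normal ranges) prior to the first dose of study drug and after the first dose of study drug".

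The protocol says who decides clinical significance. Section 8.2 states: "The Investigator will exercise his or her medical and scientific judgment in deciding whether an abnormal laboratory finding or other abnormal assessment is clinically significant". Under the same section, clinically significant findings that arise, or that were present at Screening and "significantly worsen during the study should be reported as adverse events". Protocol 9.2.1 plans listings of clinically significant laboratory abnormalities and says that the safety analysis is descriptive.

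**The concern.** The endpoint has two qualifiers, clinical significance and change from baseline, and the counting rules in SAP 3.6.2 apply neither consistently. SAP 3.6.1 treats the first primary endpoint differently: it restates drug-related AEs and then plans a count of patients with at least one. For the laboratory endpoint, no planned table counts patients with at least one clinically significant abnormality. SAP 3.6.1 also has a treatment-emergent rule for AEs, and SAP 3.6.2 has none for laboratory values.

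At stake is what the report presents as a primary safety result. A count that mixes pre-existing and chance abnormalities with important new ones is harder to read in arms of 12. Protocol 5.2 gives a warning from Phase 1: Grade 1 ALT elevations were about as frequent on placebo as on active drug, and the liver signal came from larger rises. The study is also sponsor-open, with a descriptive review after each 12 patients (Protocol 9.2.3), so a definition chosen late would be open to question.

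**Working it through.** **Step 1. Do the counting rules use baseline?** (SAP 3.6.2 table and the sentence after it; Protocol Appendix B)

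| Test | Baseline term in the rule? |
|---|---|
| ALT, AST, bilirubin, ALP | Yes: multiples of baseline if baseline was abnormal; if it was normal, exceeding ULN is itself a change |
| Hemoglobin increased | Yes: an increase is required |
| Creatinine | In part: Grades 2 and 3 include multiples of baseline; Grade 1 does not |
| Potassium, CPK, eGFR, anemia, white cells, platelets | No |
| All other tests, including glucose and urinalysis apart from the proteinuria criterion in the chronic kidney disease row | No: normal range only |

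**Step 2. Can an eligible patient be counted without any change?** Yes.

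- *eGFR.* Protocol 4.2 excludes values below 60 mL/min/1.73 m². The SAP grades values from the lower limit of normal down to 60 as Grade 1. A patient in that band at Day 1 and throughout is counted after dosing.
- *Glucose.* It is in the chemistry panel but has no CTCAE row. Protocol 4.2 excludes type 2 diabetes only if HbA1c exceeds 9%. An eligible patient with stable, raised glucose is counted after dosing.

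With 12 patients per arm (SAP 2.2.4), each such patient adds 1/12 = 8.3 percentage points to the arm's incidence.

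**Step 3. How often would one normal-range test flag a patient with no drug effect?** The documents give no rates, so the per-visit rate p is an assumption. Protocol Appendix A has eight scheduled visits after Day 1: Days 8, 15, 22, 29, 36, 43, 57 and 85. If visits are fully correlated, the proportion flagged is p. If they are independent, it is 1 − (1 − p)^8.

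At p = 5%: 1 − 0.95^8 = 1 − 0.663 = 0.337, and 12 × 0.337 = 4.0 patients. The last column counts only patients in range at Day 1. It is 0 under full correlation, because the same patients are always out of range, and (1 − p) × [1 − (1 − p)^8] under independence.

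| Assumed p | Flagged, correlated to independent | Patients of 12 | Flagged if in range at Day 1 |
|---|---|---|---|
| 1% | 1% to 7.7% | 0.1 to 0.9 | 0% to 7.6% |
| 5% | 5% to 33.7% | 0.6 to 4.0 | 0% to 32.0% |
| 10% | 10% to 57.0% | 1.2 to 6.8 | 0% to 51.3% |

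A Day 1 comparison thus removes persistent abnormalities but hardly reduces flags from visit-to-visit noise. Those need the clinical-significance qualifier, so both changes are required.

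**Step 4. Would a bare Grade 2 cut-off supply that qualifier?** Not alone. Protocol 8.1 and 9.2.3 already single out laboratory changes that can be below Grade 2 in the SAP table:

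- Platelets below 140,000: Grade 1 extends down to 75,000.
- ALP at 2 × ULN (Protocol 9.2.3): Grade 1 extends to 2.5 × ULN if baseline was normal.
- A creatinine rise of 0.3 mg/dL: this exceeds 1.5 × baseline only if baseline is below 0.3/0.5 = 0.6 mg/dL.

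Tests without a CTCAE row would have no threshold at all.

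**The case against.** The best defense is that the information is already reported elsewhere. The CTCAE sentence directly follows the endpoint and can be read as the SAP's version of it. Clinically significant findings become AEs under Protocol 8.2, and SAP 3.6.1 tabulates AEs, with Grade 2 or higher ALT as an event of special interest. Protocol 9.2.1 adds a listing. The liver rows, where Phase 1 showed a signal, use baseline. Changes from baseline are summarized by test and visit.

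Much of this stands, and it limits the point. A reader might infer that the endpoint is never computed; the documents do not support that. But the AE tables do not isolate laboratory findings in hematology, chemistry and urinalysis, the SAP does not designate them as this endpoint, and a listing is not an incidence. A descriptive primary endpoint still needs a case definition.

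Two other stronger readings also fail:

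- *Nearly every patient will be counted, so arms cannot be told apart.* That requires pooling all tests into one any-abnormality count per patient. The SAP describes no such table, grades 2 to 4 remain visible, and placebo remains the comparator.
- *The before-and-after display suggests harm because there are more looks after dosing.* The schedule is the same in every arm, so the comparison with placebo is not distorted. The SAP also does not say that pre-dose pools Screening with Day 1, and SAP 3.1.3 sets baseline at Day 1 pre-dose.

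**Conclusion.** The point holds in this form: the second primary endpoint is not defined operationally and is not tabulated as named. The stated rules also count unchanged baseline abnormalities for the CTCAE rows without a baseline term and for every normal-range test. This follows from the text alone.

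The size cannot be fixed from the documents. The 5% to 33.7% range for one test over eight visits depends on an assumed 5% rate and brackets the correlation between visits; the independent end is an upper case. It shows that a normal-range count cannot stand in for clinically significant change, and it does not predict the trial's result.

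No sample size, power or error rate is affected. The change should be made before database lock because it concerns a primary endpoint.

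**What to change.** In SAP 3.6.2:

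1. Restrict the CTCAE and normal-range counts to treatment-emergent values, meaning new or worse than the patient's Day 1 grade or value, and add shift tables from Day 1.
2. Add one table by arm, split by hematology, chemistry and urinalysis, of patients with at least one clinically significant post-dose abnormality (n/N and percentage). Exact confidence intervals are optional.
3. Define such an abnormality before database lock as either a laboratory finding that the Investigator judged clinically significant, or one that meets a prespecified threshold and is worse than Day 1. State the data source for the first limb. Findings reported as AEs under Protocol 8.2 can be identified; Protocol 8.9 describes clinical assessment of all laboratory data but no coded field, so an eCRF flag can be used only if one exists.
4. Reconcile the threshold with the laboratory criteria in Protocol 8.1 and 9.2.3, state how tests without a CTCAE row are handled, and align the table with the listing in Protocol 9.2.1.
5. Keep the existing tables as supportive.

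The cost is SAP wording and a few extra tables. The Day 1 comparison and the AE route need no new data collection.
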